### 10.1.2 Analyses of Continuous Variables

Change from baseline in PSS will be analyzed by stratified van Elteren test. For other continuous variables, the model based mean and standard error will be presented. The Baseline and visit means will also be presented for each treatment group for subjects who have both Baseline and post Baseline visit values. The treatment groups will be compared using ANCOVA with treatment group, Baseline value, and stratification factor in the model.

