**Figure 1. Study Design Schematic**

**4.3 Sample Size**

Using a two-sided Chi squared test at level of significance 5%, the sample size of 110 (2 × 55) subjects will provide 94% power assuming response rates of the primary endpoint (PASI 90 at Week 24) of 70% for risankizumab and 35% for FUMADERM®.

These assumptions are in line with what has been observed in recent studies for risankizumab (63/83 (75.9%) at Week 24) and FUMADERM® 61/273 (22.3%) of the subjects achieved PASI 90 at Week 16 in the FUMADERM® arm in the BRIDGE trial.

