**5.2 Variables Used for Stratification of Randomization**

Subjects will be randomized in 1:1 ratio to receive risankizumab or FUMADERM® stratified by prior phototherapy, with a maximum of 20% of subjects with prior phototherapy. Randomization will not be stratified by center due to the limited number of subjects per center. Randomization will be done using an adequate block size.

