## **14.0                   Summary of Changes**

### **14.1                   Summary of Changes Between the Latest Version of Protocol and the Current SAP**

In Section 10.1.2 of this SAP, the strategy for analysis of continuous endpoints was further refined. The protocol had specified ANOVA with treatment group and stratification factor in the model. The SAP now clarifies that for change from baseline in PSS a stratified van Elteren test will be used. For other continuous variables, treatment groups will be compared using ANCOVA with treatment group, Baseline value, and stratification factor in the model. This modification was done to align the study with the other studies in the Risankizumab Psoriasis development program.

In Section 10.3, NAPSI was added as a secondary endpoint to make optimal use of the data collected for NAPPA-CLIN assessments.

---

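### Change in PSS is the one continuous endpoint with no baseline covariate and no planned between-group estimate; adding the ANCOVA already in the SAP is a cheap, minor improvement

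*SAP*

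**What the plan says.** SAP 10.1.2 separates one endpoint from the rest: "Change from baseline in PSS will be analyzed by stratified van Elteren test". The other continuous variables get a model-based mean and standard error, and for them "The treatment groups will be compared using ANCOVA with treatment group, Baseline value, and stratification factor in the model".

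SAP 14.1 shows that the split is intended. It says that "for change from baseline in PSS a stratified van Elteren test will be used", confirms that the ANCOVA is for the other continuous variables, and gives alignment with the rest of the risankizumab psoriasis programme as the reason. It offers no distributional argument specific to PSS. Protocol 8.1.4 had planned a two-way ANOVA with treatment and prior phototherapy for all continuous secondary endpoints, without a baseline covariate.

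Three other places bear on the point:

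- Protocol 8.1.2 promises descriptive statistics (mean, SD, median, quartiles, range) for continuous variables.
- The proportion reaching PSS (0) at Weeks 16 and 24 is a separate secondary endpoint (SAP 10.3). It gets the stratified risk difference with 95% CI of SAP 10.1.1.
- SAP 10.4 says that secondary endpoints are not used for confirmatory interpretation.

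**The concern.** PSS is the trial's direct measure of pain, redness, itching and burning (Protocol 5.3.1.1). Its total runs from 0 to 16: four items, each scored 0 to 4 (SAP Appendix G).

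On a bounded scale, change depends on where the subject starts. Subtracting baseline imposes a slope of 1 on it; ANCOVA estimates the slope. When baseline and follow-up are only moderately correlated, the imposed slope leaves between-subject variation in the comparison that the model would remove.

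A van Elteren test also returns a p-value and no estimate. For an endpoint declared non-confirmatory, an estimate with its uncertainty is the more useful output. Other bounded scores, such as DLQI, HADS and PSSI, get ANCOVA, so the shape of the scale alone does not explain the exception.

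**Working it through.** **The plan's own figure.** The only stated power is for PASI 90 at Week 24: "the sample size of 110 (2 × 55) subjects will provide 94% power", assuming response rates "of 70% for risankizumab and 35% for FUMADERM", with a two-sided 5% chi-squared test. Exact enumeration gives 94.2% with continuity correction (Fisher's exact test also gives 94.2%) and 96.2% without; the normal approximation without correction gives 96.6%. So 94% is reproduced by the continuity-corrected version. It does not concern PSS, for which no power is stated.

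**Inputs from the documents.** 55 subjects per arm, allocated 1:1. Randomisation is "stratified by prior phototherapy, with a maximum of 20% of subjects with prior phototherapy"; at the cap, 0.20 × 110 = 22 subjects have prior phototherapy, or 11 per arm, leaving 44 per arm without. The PSS total is 4 × 4 = 16 at most.

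**Inputs not in the documents, therefore assumed.** The PSS standard deviations, the baseline-to-follow-up correlation r, the baseline and follow-up means, and the treatment effect.

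**Step 1: algebra, ignoring the floor.** Take baseline SD = follow-up SD = 1.

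- Variance of the change score: 2(1 − r).
- ANCOVA residual variance: 1 − r².
- Ratio, ANCOVA to change score: (1 + r)/2.
- Multiply by 0.955, the asymptotic efficiency of a Wilcoxon-type test against the t-test under normality, to get the efficiency of van Elteren relative to ANCOVA.

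| r | (1 + r)/2 | × 0.955 | Information lost | 110 subjects worth |
|---|---|---|---|---|
| 0.3 | 0.65 | 0.62 | 38% | 68 |
| 0.5 | 0.75 | 0.72 | 28% | 79 |
| 0.7 | 0.85 | 0.81 | 19% | 89 |
| 0.8 | 0.90 | 0.86 | 14% | 95 |

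For an effect that ANCOVA detects with 90% power, van Elteren power is Φ(√efficiency × (1.960 + 1.282) − 1.960): about 72% at r = 0.3, 78% at 0.5 and 83% at 0.7. Most of the loss comes from the fixed slope; using ranks costs about 4.5% under normality.

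If the follow-up SD is 0.75 of the baseline SD, the change variance at r = 0.5 is 1 + 0.5625 − 0.75 = 0.8125 and the ANCOVA variance is 0.5625 × 0.75 = 0.4219. The efficiency is then 0.4219/0.8125 × 0.955 = 0.50, so the loss is larger than with equal SDs.

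**Step 2: simulation on the 0–16 scale.** Scores are rounded to integers and truncated to 0–16. Before truncation: SD 3.3 at both times, baseline mean 9, control follow-up mean 4, treatment shift 1.8. There are 55 per arm, strata of 44 and 11 per arm, and 2,000 trials per setting. Truncation reduces the realised mean difference to about 1.5. Monte Carlo standard error is at most √(0.25/2000) = 1.1 points.

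| r | van Elteren | ANCOVA | Gap (points) |
|---|---|---|---|
| 0.2 | 51% | 81% | 30 |
| 0.3 | 54% | 80% | 26 |
| 0.5 | 67% | 88% | 21 |
| 0.7 | 85% | 95% | 10 |
| 0.8 | 94% | 99% | 5 |

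Under no difference, both tests reject in about 5% of trials (3.9–5.8%).

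**Step 3: a larger effect.** With a shift of 3 points before truncation, power is 87% against 99.5% (r = 0.2), 89% against 99.5% (r = 0.3) and 96% against 99.9% (r = 0.5). The gap shrinks to between 4 and 12.5 points.

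**Step 4: against the protocol's method.** In the setting of Step 2, van Elteren and the two-way ANOVA on change have 49% and 51% power at r = 0.2, 55% and 57% at 0.3, and 66% and 70% at 0.5. (This is a separate run, hence small differences from the Step 2 table.) The SAP therefore cost PSS little power relative to the protocol. What PSS lost was the mean difference that the ANOVA could supply; what it missed was the baseline adjustment that the other endpoints gained.

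**The case against.** The strongest case for leaving the plan alone is this. The choice is disclosed in SAP 14.1 with a reason. A rank test is a standard option for a short sum score that may pile up at zero. It keeps its size. The endpoint is one of many unranked, non-confirmatory secondaries, and the primary analysis is untouched. All of that stands, and it sets the priority.

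Three stronger readings are tempting, and the documents do not support them:

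- A reader might infer that the PSS analysis ignores baseline. It does not: a change score subtracts baseline for every subject. Only adjustment for baseline as a covariate is missing.
- A reader might infer that no effect size will be available. Protocol 8.1.2 provides arm-level summaries, and PSS (0) has a risk difference with CI. These are partial: PSS (0) counts only complete absence of symptoms, and arm-level summaries give no adjusted contrast with its uncertainty.
- A reader might take a large loss of precision as established. It depends on inputs that the documents do not give, and it is modest at high correlation with equal SDs or when the effect is large.

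Programme alignment is a reason to keep van Elteren. It is not a reason to omit an estimate beside it.

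**Conclusion.** The point holds as a question of efficiency and estimation, not validity. PSS change is the only continuous efficacy endpoint for which the SAP plans neither a baseline covariate nor a between-group estimate with CI.

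Under the assumptions stated (equal SDs before truncation, a shift of 1.8 points before truncation), the power given up relative to ANCOVA runs from about 30 points at r = 0.2 to about 5 points at r = 0.8, and less for larger effects. A follow-up SD below the baseline SD would increase the loss. None of these inputs can be read from the protocol or SAP, so the direction is firm and the size is conditional. The stated 94% power and the primary conclusion are unaffected. This is a cheap improvement of minor priority.

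**What to change.** Before database lock, add a sentence to SAP 10.1.2: change from baseline in PSS will also be analysed by ANCOVA with treatment group, baseline PSS and prior phototherapy, and the adjusted treatment difference will be reported with its 95% CI.

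Retain the stratified van Elteren test for comparability with the other studies in the programme. If floor effects are the worry, take the p-value instead from a stratified rank ANCOVA on baseline PSS. Either way, state in advance which p-value accompanies the estimate, and record the addition in SAP 14.1.

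The cost is one additional PSS analysis for a non-confirmatory endpoint, using a model that is already specified and data that are already collected.

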### **10.1.3 Missing Data Imputations**

Missing data will be imputed using the following methods for the efficacy analyses:

- Non-Responder Imputation (NRI): the NRI analysis will categorize any subject who has a missing value at a specific visit as a non-responder for that visit. The only exception is when the subject is a responder both before and after a specific visit window, and then the subject will be categorized as a responder for the visit. The NRI will be the primary approach in the analyses of categorical variables.
- Last Observation Carried Forward (LOCF): The LOCF analyses will use the completed evaluation from the previous visit for efficacy measures assessed to impute missing data at later visits. Baseline values will not be carried forward. LOCF will be the primary approach in the analyses of continuous variables, and the secondary approach in the analyses of categorical variables.
- As-Observed Cases (OC): The as-observed analysis will not impute values for missing evaluations, and thus a subject who does not have an evaluation on a scheduled visit will be excluded from the as-observed analysis for that visit. As-observed analysis will be the secondary approach in the analysis of continuous variables.
- Multiple Imputation (MI): The MI will be used as sensitivity approach to impute missing data in the primary endpoint. The variables to be included in the imputation model are listed below. If MI is not applicable due to the nature of our data (e.g., MCMC algorithm does not converge), this analysis will not be performed.

The Multiple Imputation analysis will be carried out in three steps.

- Imputation of missing data. The imputation will be generated for the primary endpoint measurement. The variables to be included in the imputation model are: Baseline disease severity (PASI), Baseline weight, treatment group, prior phototherapy exposure, and PASI measurements at each visit from randomization up to the end of the study. For each endpoint, 20 'complete' datasets will be generated using SAS PROC MI. The imputed

post-baseline measurements will be rounded to the same precision as the observed data before the determination of responder status (PASI 90).

- Analysis of imputed data sets. A CMH test, stratified by stratification factor, will be used to analyze categorical endpoints in each imputed dataset. Synthesis of imputation and analysis results. SAS PROC MIANALYZE will be used to generate the final inferences of the risk difference between treatment groups.

Of note, subjects who discontinued due to AE of "worsening of disease under study" will be counted as non-responders in all subsequent visits in the NRI and MI analyses, and will have their last observation prior to discontinuation carried forward in the LOCF analyses.

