### **5.4 Removal of Subjects from Therapy or Assessment**

#### **5.4.1 Discontinuation of Individual Subjects for Either Risankizumab or FUMADERM®**

A subject may withdraw from the study at any time. The Investigator may discontinue any subject's participation for any reason, including an adverse event, safety concerns or failure to comply with the protocol.

Whether randomized to risankizumab or to FUMADERM®, subjects will be withdrawn from the study immediately if any of the following occur:

1. Clinically significant abnormal laboratory results or adverse events, which rule out continuation of study drug, as determined by the Investigator and the AbbVie TA MD.
2. The Investigator believes it is in the best interest of the subject.
3. The subject requests withdrawal from the study.
4. Deviation from inclusion and exclusion criteria was noted after the subject started study drug, when continuation of the study drug would place the subject at risk as determined by the AbbVie TA MD.
5. Introduction of prohibited medications or dosages when continuation of the study drug would place the subject at risk as determined by the AbbVie TA MD.
6. Subject is non-compliant with TB prophylaxis (if applicable) or develops active TB at any time during the study.
7. The subject becomes pregnant while on study drug.
8. Subject has known malignancy, except for localized non-melanoma skin cancer. Discontinuation for carcinoma in-situ of the cervix is at the discretion of the Investigator.
9. Subject is significantly non-compliant with study procedures which would put the subject at risk for continued participation in the study in consultation with the AbbVie TA MD.
10. Occurrence of following hepatic test abnormalities considered by the investigator to be related to study drug:
  - Confirmed ALT or AST  $> 8 \times$  Upper Limit of Normal (ULN)
  - Confirmed ALT or AST  $> 5 \times$  ULN for more than 2 weeks
  - Confirmed ALT or AST  $> 3 \times$  ULN and (total bilirubin  $> 2 \times$  ULN)
  - Confirmed ALT or AST  $> 3 \times$  ULN with the appearance of fatigue, nausea, vomiting, right upper quadrant pain or tenderness, fever, rash, and/or eosinophilia ( $> 5\%$ )

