### **Definition of Analysis Windows**

All time points and corresponding time windows are defined based on Rx Days.

Analysis windows are constructed using the following algorithm:

- Determine the nominal Rx day for each visit (e.g., Week 4 [4 weeks after Baseline visit] equals Rx Day 29).

- In order to include all post baseline data, the first post-baseline interval starts on the first day after the first dose of study drug (Rx Day 2).
- Determine the window around a specific nominal Rx day by adding or subtracting half of the interval between adjacent visits (e.g., days between Week 4 and Week 8 is 28). The threshold between adjacent visits is determined by splitting the interval evenly between the visits. If the resulting split is between Rx days, then the threshold is determined as the midpoint between the adjacent visits. If the resulting split is on an Rx day, then the threshold is determined as being between that Rx day and the Rx day prior to it (e.g., the split between Week 4 and Week 8 would be between Rx Days 43 and 44).
- If more than one assessment is included in a time window the assessment closest to the nominal day will be used. If there are two observations equidistant to the nominal day, the later one will be used in analyses. If more than one assessment is included on the same day, then the worst assessment on that day will be used in analyses, except those specified in Section 11.0.

For subjects who were randomized and not dosed, the date of randomization will be used for determining window definitions.

The following analysis windows have been specified:

**Table 1. Visit Windows for Analysis of Vital Signs, PASI, BSA Involvement, sPGA, Urinalysis, Targeted Safety Laboratory Testing (ITT/Safety Populations)**

Window Label	Target Day	Interval
Baseline	1	≤ 1
Week 4	29	[2, 43]
Week 8	57	[44, 71]
Week 12	85	[72, 99]
Week 16	113	[100, 127]
Week 20	141	[128, 155]
Week 24	169	[156, 183 a ]

Rx Day calculated relative to first dose date of study drug. For subjects randomized but not dosed, Rx Day calculated relative to Randomization.

Targeted Safety Laboratory Testing includes CBC with differential count (hematology), ALT, AST, gamma-GT, alkaline phosphatase (AP) and serum creatinine.

a. For safety analyses (urinalysis and targeted laboratory testing): The minimum of upper bound and 105 or 7 days after the last dose for risankizumab and FUMADERM®, respectively.

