## 7.3 Previous Treatment and Concomitant Medications

Prior and concomitant medications will be summarized by generic name, separately for Psoriasis Therapy and other medications, per the category documented on the eCRF. A prior medication is defined as any medication taken prior to the first dose of study drug. A concomitant medication is defined as any medication that started prior to the first dose of study drug and continued to be taken after the first dose of study drug or any medication that started after the first dose of study drug, but not after the last dose of study drug. The number and percentage of subjects who had taken medications will be summarized by generic drug name assigned by the World Health Organization (WHO) for both prior and concomitant medications.

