## **7.4 Protocol Deviations**

Number and percentage of subjects who reported at least one of the following protocol deviation categories will be provided.

- Subject entered into the study even though she/he did not satisfy entry criteria
- Subject who developed withdrawal criteria during the study and was not withdrawn
- Subject who received wrong treatment or incorrect dose
- Subject who received excluded or prohibited concomitant treatment

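### No planned sensitivity analysis tests PASI values observed after other psoriasis therapy began, and SAP 7.3 stops counting such therapy 56 days before Week 24 for risankizumab completers only

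*SAP*

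**What the plan says.** **Scoring.** Under SAP 10.1.3 the primary rule acts on missing values: "the NRI analysis will categorize any subject who has a missing value at a specific visit as a non-responder for that visit". One rule overrides observed data. Subjects who discontinue for an adverse event of worsening psoriasis "will be counted as non-responders in all subsequent visits in the NRI and MI analyses", and in LOCF their last value before discontinuation is used. Assessments are assigned to visits by date alone: "All time points and corresponding time windows are defined based on Rx Days". The Week 24 PASI window is Days 156 to 183 (SAP 6.0, Table 1).

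**Sensitivity analyses.** SAP 10.2 names LOCF and MI for the primary endpoint. The MI model uses "PASI measurements at each visit from randomization up to the end of the study". Protocol 8.1.1 allows, but does not require, a per-protocol analysis; SAP 5.1 defines only the ITT and Safety populations.

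**Other therapy.** Protocol 5.2.3.3 (Table 1) bans other psoriasis treatment during the study, with an exception for urgent treatment of a flare (footnote a). The stated reason for the ban includes protecting the efficacy outcome. Withdrawal is required under Protocol 5.4.1 item 5 for "Introduction of prohibited medications or dosages when continuation of the study drug would place the subject at risk", so not for every breach. The same section asks for the early termination (ET) visit within 2 weeks of the decision to stop, and before new therapy only as a preference.

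**Reporting.** SAP 7.3 summarizes medications "separately for Psoriasis Therapy and other medications, per the category documented on the eCRF". Of medications begun during the study, it counts as concomitant "any medication that started after the first dose of study drug, but not after the last dose of study drug". SAP 7.4 has one deviation category, "Subject who received excluded or prohibited concomitant treatment", with no timing.

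**The concern.** A subject who starts a banned psoriasis drug need not be withdrawn. If that subject has a PASI on Days 156 to 183 showing at least 90% improvement, it counts as a response to the assigned arm. PASI 90 at Week 24 is the only confirmatory endpoint, and the trial is open label: the investigator who would add therapy knows the allocation, even though the efficacy assessor does not.

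Extra responders on FUMADERM narrow the risk difference; extra responders on risankizumab widen it. A reader would want to know how many subjects were involved, in which arm, and whether the result depends on them. The SAP as written plans no analysis that answers the last question, and its medication summary would answer the first two over different periods in the two arms.

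**Working it through.** **1. The plan's own figure.** Inputs from SAP 4.3: 55 per arm, 70% against 35%, two-sided 5%, stated power 94%. The uncorrected chi-squared approximation gives 96.6% (exact enumeration 96.2%), the continuity-corrected form 94.8%, and Fisher's exact test 94.2%. The stated 94% is therefore reproduced by the corrected or exact variant.

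**2. Which subjects can affect the primary analysis.** Only those with an observed PASI on Days 156 to 183. An ET visit before Day 156 leaves Week 24 missing, and NRI scores non-response. With ET up to 14 days after the decision to stop, the earliest decision that can place an ET value in the window is Day 156 − 14 = Day 142. The other routes are a subject who takes a banned drug and is not withdrawn, urgent flare therapy, and a subject off study drug but still in the study.

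**3. Which planned analyses would react.**
- NRI (primary): keeps the observed value.
- LOCF: keeps it, and can also carry an ET value taken on new therapy to later visits.
- MI: keeps it, and uses it in the imputation model.
- As-observed (secondary method for continuous endpoints): does not carry the ET value forward, but keeps any value observed in the window.
- Per-protocol: not in the SAP.

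None compares PASI 90 with and without these values.

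**4. Size per subject.** 1/55 = 1.8 percentage points. The number of such subjects is not in the documents; 1 to 5, all in one arm, is an assumption for illustration. Power by enumeration is the sum over x and y of b(x; 55, p1) × b(y; 55, p2) for all outcomes with |z| > 1.96, where z is (x − y)/55 divided by its standard error. The pooled standard error gives the chi-squared test; the unpooled one gives the SAP 10.1.1 risk-difference test, here without strata. The risankizumab rate is held at 70%.

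| Extra FUMADERM responders | FUMADERM rate | Difference | Chi-squared, exact | Risk difference, exact | Continuity-corrected |
|---|---|---|---|---|---|
| 0 | 35.0% | 35.0 | 96.2% | 96.4% | 94.8% |
| 1 | 36.8% | 33.2 | 94.2% | 94.5% | 92.2% |
| 2 | 38.6% | 31.4 | 91.5% | 92.0% | 88.7% |
| 5 | 44.1% | 25.9 | 78.6% | 80.2% | 73.0% |

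If the extra responders were all on risankizumab, the difference would become 35 + 1.8 = 36.8 points (one) to 35 + 9.1 = 44.1 points (five).

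**5. The cited FUMADERM rate instead of 35%.** 61/273 = 22.3% (Week 16, SAP 4.3). Five extra responders give 22.3 + 9.1 = 31.4%. The difference moves from 47.7 to 38.6 points and exact chi-squared power is still 98.5%. In that case mainly the estimate is affected.

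**6. The reporting cutoff.** A risankizumab completer has the last dose at Week 16, Day 113. A FUMADERM completer has it on the morning of the Week 24 visit, Day 169 (Protocol Table 5 footnote). 169 − 113 = 56 days. Psoriasis therapy started in those 56 days is outside the SAP 7.3 definition for risankizumab completers and inside it for FUMADERM completers.

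**The case against.** The strongest reply is that the choice is largely made already. The ITT population is analyzed as randomized (SAP 5.1), imputation applies only to missing values (Protocol 8.1.4, SAP 10.1.3), and Protocol 8.1.1 leaves exclusion of major deviators to an optional sensitivity analysis. A programmer would have no doubt what to do. This stands, and it is why the primary analysis should stay as it is. It does not cover the sensitivity side, because the SAP does not take up the per-protocol option.

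A second reply is that the route is narrow. The investigator may discontinue a subject for failing to comply with the protocol, intentional deviations are not allowed (Protocol 7.0), and early leavers are non-responders through missing data. This also stands and limits the reach, although none of it forces withdrawal. If FUMADERM subjects receive more added therapy, the present rule is conservative for superiority.

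A third reply is that the tables and listings are specified in a separate document (SAP 17.0), which may show what SAP 7.3 leaves out. That cannot be checked here. The point rests on the SAP's written definition, and it concerns a descriptive table.

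A reader might go further and infer that PASI after other therapy must be scored as non-response in the primary analysis. The documents do not support that. Keeping observed values is a legitimate ITT choice, no frequency is given, and such a rule would lower the rate in whichever arm received more added therapy. That would favor the sponsor's drug if the arm is FUMADERM.

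**Conclusion.** The point holds as a gap in sensitivity analysis and reporting. As written, the SAP keeps every PASI observed after another psoriasis therapy starts, apart from the worsening-disease rule, and no planned analysis shows whether the Week 24 result depends on this. LOCF, the primary method for the continuous secondary endpoints and a sensitivity method for PASI 90, can carry forward a value produced by a different drug. The SAP 7.3 cutoff treats the arms unequally over the 56 days before the primary assessment.

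The size is 1.8 points per affected subject. Any total rests on an assumed count; 1 to 5 in one arm gives shifts of 1.8 to 9.1 points. The power figures further assume the design rates and ignore the phototherapy stratum.

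It would be wrong to read this as evidence that the primary result will be biased in a known direction. The documents give neither the frequency of added therapy nor the arm in which it would be more common.

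**What to change.** Leave the primary NRI analysis unchanged and add three items to the SAP before database lock.

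1. **Sensitivity analysis of PASI 90 at Week 24.** Score a subject as a non-responder at every assessment after the start of any prohibited systemic psoriasis therapy or photochemotherapy, including urgent flare therapy. For phototherapy and prohibited topical treatment, score non-response only at a visit within 14 days after use. These two share one row and one interval in Protocol Table 1, so they should be handled alike. Use permitted by footnotes b and c is exempt.
2. **LOCF.** Carry forward the last post-baseline value before new psoriasis therapy began, extending the rule that SAP 10.1.3 already has for worsening disease. Where there is none, as can happen for endpoints measured only at Weeks 16 and 24, keep the observed value and flag it.
3. **Reporting.** Define on-study psoriasis therapy by start date up to the Week 24 assessment in both arms, not by last study dose. Tabulate by arm how many subjects started it before that assessment.

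The cost is small: a short SAP paragraph, one derived flag, one sensitivity table and one count. Start and end dates (Protocol 5.2.3.2) and the psoriasis-therapy category (SAP 7.3) are already collected. The downside is slightly more programming and a sensitivity result that may favor either arm.
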